3.6 Exploratory endpoints - N/A

3.7 Table of objectives and outcome measures

Objectives	Outcome Measures	Timepoint(s) of evaluation of this outcome measure (if applicable)
Primary Objective Does Sambucol reduce the severity of symptoms by 30% at day 10 in people who are symptomatic with the SARS-CoV-2 (COVID-19) virus?	Patient Wellness VAS score	Day 10 score
Secondary Objectives Reduction in admission to hospital by day 28. Reduction in the severity of symptoms at day 3, 7, 14 and 28 days To determine of those admitted to hospital the number of patients with mild/moderate disease progressing to severe disease (ITU /HDU admission)	Admissions to hospital Wellness VAS score Number admitted to HDU/ITU	Within 28 days of enrolment Day 3,7, 14 and 28 Day 28 data

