3.5 Secondary endpoints

Reduction in hospital admissions by day 28 as measured by rates of hospital admission

Reduction in the severity of symptoms at day 3, 7, 14 and 28 days as measured by wellness VAS Scale.

Reduction in the number of patients with mild/moderate disease progressing to severe disease (ITU /HDU admission)

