7.8 Long term follow-up assessments

With the exception of any pregnancy outcomes, Data collection will end at day 28 following randomisation. Research team will follow up the outcomes of any notified pregnancies.

This will be to check to see if patients have been admitted to hospital in the 28 days following a positive SARS-CoV2 test.

If admitted:

- Date of hospitalisation
- Admission hospital and location (i.e. HDU/ITU) – reason and outcome. Date discharge / death

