10 STATISTICS AND DATA ANALYSIS

10.1 Sample size calculation

The sample size was based on detecting a difference in the primary outcome, VAS symptoms score at 10 days, between groups. The standard deviation of the outcome is estimated to be 20 units, and a difference between groups of 10 units is regarded as being of clinical importance. With a 5%

BERRY Protocol v 6.2 22.07.2021 IRAS 282732

significance level and 90% power, it is calculated that 86 patients per group, 172 in total, are required. To allow for a 15% dropout, it is proposed that 204 patients are recruited into the study.

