10.3.3 Secondary outcome analysis

Secondary outcomes with a baseline measurement at baseline will be analysed using equivalent methods to the primary outcome. Secondary endpoints measured on a categorical scale will be compared between groups using the Chi-square test.

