10.7 Participant population

The primary analyses for all analysis (primary, secondary, safety) will be done on an ITT basis, with patients included in the groups to which they were randomised, irrespective of whether they received their allocated treatment.

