10.8 Procedure(s) to account for missing or spurious data

Spurious data will be identified and checked with original source documentation. If found to still be spurious, based on clinical values may be excluded from the analysis. Any omissions will be noted and justified.

Patients with missing data for any given variable will be omitted from the analysis. No imputations of missing data will be performed.

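### HDU/ITU progression has no stated denominator, and Table 3.7 words it among admitted patients, a group formed after randomisation

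*Combined protocol and SAP*

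**What the plan says.** The endpoint appears in two places in the protocol, with different wording.

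- **Section 3.5 (Secondary endpoints):** "Reduction in the number of patients with mild/moderate disease progressing to severe disease (ITU /HDU admission". There is no restriction to admitted patients.
- **Table 3.7:** "To determine of those admitted to hospital the number of patients with mild/moderate disease progressing to severe disease". The outcome measure listed for this objective is "Number admitted to HDU/ITU", evaluated on day 28 data.

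The rules that would govern its analysis are general ones.

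- **Section 10.3.3:** "Secondary endpoints measured on a categorical scale will be compared between groups using the Chi-square test". No denominator is named.
- **Section 10.7:** "The primary analyses for all analysis (primary, secondary, safety) will be done on an ITT basis", with participants kept in the arm to which they were randomised.
- **Section 10.8:** "Patients with missing data for any given variable will be omitted from the analysis", without imputation.
- **Section 7.8:** the ward or unit, including HDU/ITU, is recorded under a list that applies only if the participant was admitted.

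Section 10.3 defers detail to a full SAP to be agreed before any analysis. The endpoint is not among the secondary objectives in section 3.2 or the trial summary.

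**The concern.** Participants are outpatients at entry, so hospital admission happens after randomisation. It is also a secondary endpoint that the trial hopes to reduce. If the treatment prevents mainly the milder admissions, the admitted patients in the active arm are a sicker selection than those in the placebo arm. A comparison of HDU/ITU shares between those two selections is no longer protected by randomisation.

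A chi-square test needs non-events as well as events, so someone must choose a denominator. The only population named specifically for this endpoint is the admitted, in Table 3.7. If that wording is followed, or if the choice is left until the data have been seen, the trial could report a higher severe share on active treatment when no more participants became severely ill.

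**Working it through.** **1. The plan's own figure.** The only calculated figure is the sample size in section 10.1 (difference 10, SD 20, 5% significance, 90% power). The two-sided normal approximation gives 2 × (1.960 + 1.282)² × 20²/10² = 84.1, or 85 per group. The t-based calculation gives 85.03, which rounds up to the stated 86. With 15% dropout, 86/0.85 = 101.2, or 102 per arm and 204 in total. The plan's figure reproduces. It concerns the VAS score and supplies only the 102 per arm used below.

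**2. Assumptions.** The documents give no admission or HDU/ITU rates. All rates here are assumed:
- placebo admission *a* = 5%, 10% or 20%;
- share of placebo admissions reaching HDU/ITU *s* = 20%;
- admissions cut by *c* = 30% or 50%;
- HDU/ITU cases cut by *h* = 0% (only milder admissions prevented) or 20%.

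**3. Formulas.**
- Among the admitted: placebo *s*; active *s*(1 − *h*)/(1 − *c*).
- Among all randomised: placebo *a* × *s*; active *a* × *s* × (1 − *h*).

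The share among the admitted looks worse on active whenever *h* is smaller than *c*, whatever the value of *a*.

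**4. Results.**

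| *c* | *h* | Admitted: placebo | Admitted: active | Randomised, *a* = 10%: placebo | Randomised, *a* = 10%: active |
|---|---|---|---|---|---|
| 30% | 0% | 20.0% | 0.20/0.70 = 28.6% | 2.0% | 2.0% |
| 50% | 0% | 20.0% | 0.20/0.50 = 40.0% | 2.0% | 2.0% |
| 30% | 20% | 20.0% | 0.16/0.70 = 22.9% | 2.0% | 1.6% |
| 50% | 20% | 20.0% | 0.16/0.50 = 32.0% | 2.0% | 1.6% |

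With *h* = 0 the proportions per randomised participant are equal at every admission rate: 1.0%, 2.0% or 4.0% in both arms. In the last two rows the treatment helps on the randomised denominator and looks harmful on the admitted one.

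**5. The count.** An HDU/ITU patient is a hospital inpatient, so the number of HDU/ITU cases per arm is the same with or without the restriction. With *a* = 10% and *h* = 0 it is 102 × 0.10 × 0.20 = 2.04 in each arm.

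**6. Would a test be reversed?** The largest of these scenarios with *h* = 0 is *a* = 20%, *c* = 50%. Rounded to whole patients, it is 4 of 20 admitted on placebo and 4 of 10 on active. The uncorrected chi-square is 30 × (4 × 6 − 16 × 4)²/(20 × 10 × 8 × 22) = 48,000/35,200 = 1.36, p about 0.24. The point estimate doubles, but the test shows no significant difference.

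**7. Information in the endpoint.** Expected placebo HDU/ITU cases are 102 × (1%, 2%, 4%) = 1.0, 2.0 and 4.1. For a halving, power is approximately Φ[(|p₁ − p₂| − 1.96 × SE under no difference)/SE under the difference], with 102 per arm. It is about 6%, 8% and 13%. The approximation is rough with so few events, but power is clearly low.

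**The case against.** A reader might infer that the protocol analyses HDU/ITU progression only among admitted patients and that this analysis can reverse the trial's conclusion. The documents do not support that reading.

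- The outcome measure in the same table is a count, and both wordings of the endpoint speak of a number of patients. The count cannot show a false worsening.
- Neither 3.5 nor 3.7 states a denominator, and 10.3.3 does not direct its test to an admitted subset.
- Section 3.5 is unrestricted and 10.7 requires ITT. Read together, they favour all randomised participants.
- The phrase in 3.7 may simply mirror data capture, since location is recorded only for those admitted.
- The distortion depends on assumed rates and, in the scenario tested above, affects a point estimate without producing a significant result.

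All of this stands, and it limits the point to a conflict of wording with an undefined denominator. It does not remove it. Section 10.7 fixes the arm in which a participant is analysed, but does not say that someone never admitted counts as not having reached HDU/ITU. Because location is collected only on admission and 10.8 drops participants with a missing value, a literal application could leave only the admitted in the analysis. The promised SAP could settle this, but nothing in the present text does.

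**Conclusion.** The point holds as an inconsistency. Table 3.7 names the admitted as the population, 3.5 does not, 10.7 calls for ITT, and the chi-square denominator is unstated. If the admitted were used, the estimate could mislead. It would be 20% against 28.6% to 40% with equal HDU/ITU counts, and 20% against 22.9% to 32.0% even when severe cases fall by a fifth. These figures rest on assumed rates and on treatment reducing admissions proportionately more than HDU/ITU cases.

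The consequence is modest. With about 1 to 4 placebo cases expected and 6% to 13% power for a halving, the endpoint is descriptive at best under either definition. The primary VAS analysis, the comparison of admissions, the raw HDU/ITU count and the sample size are unaffected. The correction is still worth making, because it prevents a misleading severity signal and a denominator chosen after the data are seen.

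**What to change.** - **Table 3.7:** remove the restriction to admitted patients from this objective so that it matches 3.5.
- **Section 10.3.3 and the SAP:** define the endpoint as HDU/ITU admission by day 28 (yes or no), with all randomised participants with follow-up as the denominator, analysed in the randomised arm.
- **Coding:** record participants known not to have been admitted as no. A blank location field is then not treated as missing under 10.8, and only participants whose admission status is unknown are omitted.
- **Window:** state the starting point of the 28 days. Table 3.7 counts admissions from enrolment, while section 7.8 says "This will be to check to see if patients have been admitted to hospital in the 28 days following a positive SARS-CoV2 test".
- **Reporting:** give the count per arm with the randomised denominator. Any breakdown among the admitted is descriptive, without a test.

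The cost is one phrase in 3.7 and a short definition in a SAP that has yet to be written. The data collected and the sample size do not change.

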4 TRIAL DESIGN

This study is a superiority test of Sambucol to placebo in the treatment of COVID 19 positive patients, with a parallel design.

Single Centre, placebo controlled, single blinded, two arm, randomised controlled trial.

5 TRIAL SETTING

This trial will run as a single centre trial at East Kent Hospitals University Foundation Trust. Secondary care patients will be highlighted from the positive COVID 19 swab lists. These lists include all patients attending swabbing centres or accident and emergency departments in the trust, but who are not admitted. Eligibility, consent and randomisation will be completed by GCP trained research nurses and doctors

: Participants will also be identified at local swabbing sites. Members of the Research Team will be there to approach and discuss the trial with people attending for swabbing.

Participants may also contact the research team after seeing the approved posters or hearing about the trial through other external sources eg the media.

6 PARTICIPANT ELIGIBILITY CRITERIA

6.1 Inclusion criteria

- Aged over 18 years
- Symptomatic SARS-CoV2 infection
- Positive SARS-CoV2 swab test result within the last 5 days
- Capacity to provide written or electronic informed consent
- Able to complete follow up visits required via phone/email
- Able to provide a positive swab result

6.2 Exclusion criteria

- Known allergy to Sambucus fructi (Elderberries) or food colourants
- Pregnant or breast feeding
- Poorly controlled diabetes
- Treatment with any immunosuppressive medicines including Prednisolone 10mg daily or equivalent. Oral anti-inflammatory medicines such as Ibuprofen are allowed.
- Participation in any COVID 19 research study involving prophylactic or therapeutic IMPs in the last 30 days.
- Previous participation in this trial.
- Already taking Sambucol or any form of elderberry supplement

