2.1 Assessment and management of risk

We anticipate this to be low risk trial given that Sambucol® Black Elderberry Original Liquid (*Sambucus nigra*) has never had reported adverse events/effects since commencing manufacture in 1991.

A thorough literature review has demonstrated there are no recorded side effects or drug interactions. Due to this it is classified as a food supplement and can be purchased freely without consultation or prescription, in food health shops and supermarkets, without limitation.

Vomiting and diarrhoea has been reported with the consumption of large volumes of raw and unripe fruit.

As with any product there is a potential allergy to the ingredients, hence those with known allergy will be excluded. As with all medicines, patients will be advised to seek urgent medical help if there are any signs of a severe allergy (i.e. difficulty breathing, swelling face/lips/ tongue).

With limited data on the effect in pregnancy and breast feeding this patient group has been excluded. Poorly controlled diabetics will be excluded due to the high sugar content.

The dose used is constant with no increments.

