Follow up telephone call within 5 days of a positive swab; Verbal Consent and Baseline data collection	Opportunity to raise and discuss any questions about the trial or PIS ^(a) . Eligibility criteria will be checked and electronic or verbal consent will be received. An eligible patient can decline to participate without having to give any reason. After consent, the research team will collect baseline demographics, VAS score, patient symptoms. ^(a)
Ineligible patients	If anyone does not meet the eligibility criteria the research team will explain why and ensure that they have time to ask any questions.
Randomisation and collection of trial treatment	Patients will be randomised to active or placebo liquid and a 14 day supply of study liquid dispensed to take home and start straight away. This can either be collected by a family member or friend and dropped to the patient's doorstep – or the research team will drop to the doorstep so that everyone has a chance to take part. If a participant lives further away the liquid will be delivered to their home address by courier.
Follow Up visits on day 3, 7, 10, 14 and 28	All follow up visits will occur either by phone, text or email depending on participant preference at day to collect the following data: 
 • Current symptoms

BERRY Protocol v 6.2 22.07.2021 IRAS 282732

	
 • How well are you feeling VAS score 0 -100 (0 will be recorded in the case of death) • What are your current symptoms? • Have you started any new medications? • Have you missed any doses of your study liquid? • Experienced any adverse events? • At day 14 – if a participant verbally consented initially, they will be asked to sign a paper consent form which was sent out with their trial liquid and return it in the research team for filing. At day 14 they will also be reminded that they need to stop taking their study liquid.
Notes	(a) This limits the exposure of the research team to the virus during later collection of written consent

BERRY Protocol v 6.2 22.07.2021 IRAS 282732

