7.1 Recruitment

Once patients notify the research team that they are happy to be contacted after a positive swab, the research team will then call the patients at home to see if they are still interested in taking part and send out the information sheet via email if they did not receive it at the swabbing station. If the patient does not have an email address they can arrange collection of the information sheet from site or it can be read out over the phone to them. Once they have had time to consider all the information and wish to take part, the research team will check all inclusion / exclusion criteria and eligibility. If they are not eligible the research team will explain why and ensure they have time to ask any relevant question they may have. If patients are eligible but decline they can do so without any reason.

For eligible patients wishing to take part, a link for an electronic consent form will be sent via email for e-signing. If this is not possible for any reason, then verbal consent will be taken over the telephone with the patients and two members of the research team. This will be recorded on a telephone consent form which will be read fully by the research team to the patients before consent is received. A copy of the telephone consent form will be sent to the patient's home with their randomised trial liquid. Enclosed will also be a blank copy of the full written consent form to send back via free post envelope supplied.

After consent research team will collect basic demographics, baseline VAS scores and check the patient's symptoms.

Eligible patients will be randomised 1:1, with no stratification, to either active treatment or placebo using REDCap software and be provided with the relevant bottles at full dosage, for 14 days. Dosage instructions will be provided on the labelling and will be discussed by the research team over the telephone prior to randomisation. Participants will have a contact number to contact the research team if they need to ask questions at any time.

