7.3.1 Method of implementing the randomisation/allocation sequence

- Following consent, randomisation will be via REDCap using a randomisation list generated by the study statistician and uploaded onto REDCap.
- Team members are provided with login details and randomise patients by simply completing an on-screen form with patient details, inclusion and exclusion criteria. Treatment allocation is immediately available.

Investigators can view the details of patients they have previously randomised.

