7.5 Emergency Unblinding

In case of serious adverse event, when deemed necessary by the investigator or treating health care professional, unblinding may be requested. A designated number will be provided on hospital systems and to patients in case unblinding needs to be performed by the research team. The CI will be contactable by the research team if necessary. It is thought unlikely unblinding will need to occur unless a new allergic reaction occurs to the food colouring in the liquid.

Documentation of the unblinding process including the reason and person who performed the unblinding, will be recorded in the site file. Thereby retaining the blinding of the outcome assessors.

An alert will be placed on the patient administration system (PAS) for the trust to advise clinicians that the participant is on the BERRY trial including contact details of who to contact for unblinding in an emergency. An assessment to unblind should be made in consultation with the clinical and research teams. If the decision is made to unblind the participants randomisation to the health professional, it will be expressed that the participant should not be given this information and that it should be shared only on a need to know basis. The medical team will be advised to document the act of unblinding in the patient notes, but not the randomised arm unless this is deemed essential for the participants ongoing care. This will maintain overall blinding in the trial. The treating health care professional will continue to deal with the participant's medical emergency as appropriate.

In all cases the Investigator will evaluate the causality and expectedness of SAEs as though the participant was receiving the active medication.

Unblinding and the reasons for doing so will be recorded on the CRF/data collection tool, in the site file and medical notes. It will also be documented at the end of the trial in any final trial report and/or statistical report

The CI/Investigating team will notify the Sponsor in writing as soon as possible following the unblinding and CI/PI will also notify the relevant authorities.

SUSARs are required to be reported unblinded.

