8 TRIAL TREATMENTS

8.1 Name and description of treatments

Sambucol® Black Elderberry Original (Sambucus nigra) Liquid

Constituents: 29.4 % (w/w) Black Elderberry (Sambucus nigra) fruit juice, 70% (w/w) of glucose syrup.

The main ingredient is black elderberry juice and it meets the requirements of the Directive

BERRY Protocol v 6.2 22.07.2021 IRAS 282732

2012/12/EU relating to fruit juices. The product also contains two food additives: citric acid (E330) as acidity regulator and potassium sorbate (E202) as preservative.

Primary packaging: Plastic PET amber bottles 120ml. Caps are PP28 white tamper-proof caps with security seal.

Secondary Packaging: None. Outer Carton: Cardboard 376mm x 191mm x 116mm. 32 bottles per case.

Placebo for Sambucol® Black Elderberry Original (Sambucus nigra) 120ml

Constituents: 70% (w/w) of glucose syrup, Flavouring agent: Elderberry Blossom. Colourants: Eurocert Carmoisine (311804) (E-122) and Eurocert Brilliant Black PN (419358) E-151. The product also contains two food additives: citric acid (E330) as acidity regulator and potassium sorbate (E202) as preservative.

Primary packaging: Plastic PET amber bottles 120ml. Caps are PP28 white tamper-proof caps with security seal.

Secondary Packaging: None. Outer Carton: Cardboard 376mm x 191mm x 116mm. 32 bottles per case.

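### The allergy exclusion in 6.2 is narrower than the safeguard stated in 2.1: three constituents of both trial liquids are not covered

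*Combined protocol and SAP*

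**What the plan says.** The risk assessment in 2.1 states: "As with any product there is a potential allergy to the ingredients, hence those with known allergy will be excluded". It sets no limit on which ingredients are meant.

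The exclusion list in 6.2 has one allergy criterion: "Known allergy to Sambucus fructi (Elderberries) or food colourants".

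Section 8.1 gives the composition of the two liquids. The active liquid is elderberry juice and glucose syrup. The placebo entry begins "Constituents: 70% (w/w) of glucose syrup, Flavouring agent: Elderberry Blossom" and goes on to two colourants, E-122 and E-151. The same sentence on additives appears under both liquids: "The product also contains two food additives: citric acid (E330) as acidity regulator and potassium sorbate (E202) as preservative".

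On the use of the criteria, the procedures table in section 7 says of the follow-up telephone call: "Eligibility criteria will be checked and electronic or verbal consent will be received". Section 7.3.1 has team members "randomise patients by simply completing an on-screen form with patient details, inclusion and exclusion criteria". Section 7.1 then says: "Eligible patients will be randomised 1:1, with no stratification, to either active treatment or placebo using REDCap software".

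The only other place that names an allergic cause is 7.5: "It is thought unlikely unblinding will need to occur unless a new allergic reaction occurs to the food colouring in the liquid".

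**The concern.** The low-risk assessment in 2.1 depends partly on an exclusion, and 6.2 is where that exclusion is put into effect. If 6.2 names fewer substances than 2.1 assumes, someone working through the list could pass a person whom 2.1 says is kept out, for example someone with a known hypersensitivity to sorbate. Dosing is at home, from bottles collected or delivered to the door, so the eligibility call is the natural point to catch this.

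What is at stake is participant safety for a small number of people, and agreement between two parts of the protocol. The estimand, the sample size and the analysis are not touched.

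**Working it through.** The documents give no figure for this point, so there is nothing to reproduce. The check compares the composition in 8.1 with the criterion in 6.2.

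| Constituent (8.1) | Active | Placebo | Named in 6.2? |
|---|---|---|---|
| Elderberry juice | yes | no | yes |
| Colourant E-122 | no | yes | yes |
| Colourant E-151 | no | yes | yes |
| Glucose syrup | yes | yes | no |
| Citric acid (E330) | yes | yes | no |
| Potassium sorbate (E202) | yes | yes | no |
| Elderberry blossom flavouring | no | yes | not literally |

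1. Distinct constituents across both liquids: 7.
2. Covered by 6.2: elderberry juice, E-122 and E-151, so 3. Not covered: 7 − 3 = 4.
3. Constituents in both liquids: glucose syrup, E330 and E202, so 3. Covered by 6.2: 0 of 3. Section 8.1 describes E330 as an acidity regulator and E202 as a preservative, so neither falls under colourants.
4. The flavouring depends on how 6.2 is read. The criterion names the fruit, and the flavouring is described as blossom. A generous reader would include it; a literal one would not. The three shared constituents are left out on either reading.

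Three other places could have closed the gap:

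- **Diabetes exclusion (6.2).** According to 2.1 and 8.8, this is there because of the sugar content. It deals with the syrup as a metabolic load and does not address allergy.
- **Investigator discretion.** Neither 6.1 nor 6.2 has a general criterion of this kind.
- **Baseline and screening data (7.6, 7.7).** Medical history is collected, but no allergy item is listed.

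So no other eligibility criterion extends the allergy exclusion. The wider statement stands only in 2.1.

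No expected count can be worked out. That would need the frequency of known allergy to these constituents, which the documents do not give.

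**The case against.** The strongest reply is that 2.1 is itself current protocol text. Section 13.5 requires compliance with the protocol as a whole, so staff told of a sorbate allergy could exclude the person on the strength of 2.1. Eligibility is handled by research nurses and doctors trained in good clinical practice, medical history is taken at screening, and the patient can raise a known allergy on the same call or decline to take part. This stands. A reader might infer from 6.2 that staff would have no ground to refuse such a person, or that the plan is to enrol people with known allergies. The documents do not support either inference.

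A second reply is that the information sheet or the on-screen form may list the constituents or ask about any ingredient. That is possible. Neither text is available for this review, so it cannot be said that such a person would in practice be admitted. It can be said that 6.2, applied as written, does not prompt the question.

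A third reply is that 6.2 simply names the allergens the sponsor thought relevant, and that colouring is the one 7.5 foresees. Colourants are indeed rightly covered. Nothing in the documents singles out glucose syrup, citric acid or sorbate as an allergy concern. But 2.1 speaks of the ingredients without restriction, and 6.2 already reaches beyond the active ingredient to placebo excipients, so the narrower list is not explained.

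Other safeguards exist: advice to seek urgent help (2.1), contact with the research nurse (8.7) and withdrawal by the physician (7.10). The first two work after a dose has been taken. Withdrawal could come earlier, while the liquid is still to be collected or delivered. They limit the consequence but do not replace the entry check. Section 9.2 also leaves symptoms such as wheezing and skin rash unrecorded as adverse events because they are known features of COVID-19, so a reaction of that kind might not be noticed as one.

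**Conclusion.** The point holds as a minor safety-consistency correction of the lowest severity. The operative criterion in 6.2 is narrower than the safeguard in 2.1. It leaves out three constituents present in both liquids and, on a literal reading, the placebo flavouring.

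The mismatch in wording is certain, because it rests on the text of 2.1, 6.2 and 8.1 alone. Its practical effect is not certain, because staff can rely on 2.1 and because the information sheet and form wording are unseen.

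A reader might take the fact that every participant receives the shared constituents, whichever arm they are in, as a measure of risk. It measures exposure only. With no allergy frequency in the documents, the number affected cannot be computed; it is likely to be very small. No power figure, estimate or test in the plan changes.

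**What to change.** Reword the allergy criterion in 6.2 as: *Known allergy or hypersensitivity to any constituent of either trial liquid listed in 8.1.* Put one pooled list of constituents on the eligibility form and read it out at the existing call, before randomisation. Do not attribute any constituent to an arm. The check comes before allocation and the list is the same for everyone, so it tells the participant nothing about the bottle they will receive. The bottle labels can stay as they are.

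The cost is a one-line amendment and one question on a call that already takes place. Under 13.10 the amendment needs sponsor agreement and then submission to the HRA and REC. It does not justify a stand-alone submission and can be bundled with another amendment. No test, visit or member of staff is added, and the effect on recruitment should be negligible.
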